Hemophilia B is an X-linked recessive bleeding disorder that affects approximately 1 in 20,000 to 25,000 male births. The disease is characterized by frequent, spontaneous internal bleeding that can lead to chronic arthropathy (joint damage), intracranial hemorrhage, and even death. It is caused by mutations in the factor IX (FIX) gene leading to deficiencies in coagulation. Depending on the residual activity of FIX, disease severity is classified as mild (>5% to <40% of normal), moderate (1% to 5% of normal), or severe (<1% of normal) [White 2001]. Factor IX gene therapy is expected to be effective for prevention of bleeding subjects with moderate to severe hemophilia B.

Study 101HEMB01 is a dose-finding study. A bivariate continual reassessment method (bCRM) [Braun 2002] is used in this study for the purpose of dose finding. Bearing the characteristics of adaptive design, bCRM not only addresses limitations in the historically simplistic phase I (3+3) design, it also incorporates efficacy information into consideration when identifying dose escalation. Therefore, it is well suited for the rare disease such as hemophilia B where all evaluable information from the patients should be utilized.

This statistical analysis plan (SAP) is based on the clinical study protocol 101HEMB01, version 04 dated 03Sep2015 and its associated electronic case report forms (eCRF). This document describes the rules and conventions to be used in the dose selection, analysis and representation of safety and efficacy data as presented in the clinical protocol.

2. Study Objectives and Endpoints

The study objectives and endpoints are presented in [Table 2-1](#).

Table 2-1 Study Objectives and Endpoints

Objective	Endpoint
Primary	
To determine the safety of single ascending intravenous (IV) doses of DTX101 in adults with moderate/severe to severe hemophilia B.	The incidence of adverse events (AEs), treatment-emergent adverse events (TEAEs), and serious AEs will be summarized for each dosing cohort by severity and relationship to study product.
To establish a dose of DTX101 that achieves a peak plasma level of vector-derived factor IX (FIX) at 6 weeks after IV administration to allow further clinical development.	Peak plasma level of vector-derived factor IX (FIX) at 6 weeks after IV administration as determined by the activated partial thromboplastin time (aPTT) clot-based assay.

Objective	Endpoint
Secondary	
To assess the impact of DTX101 on the number of bleeding episodes requiring recombinant FIX infusion during the study.	The annualized bleeding rate (ABR) will be calculated for all subjects through Week 52 (± 7 days).
To evaluate the kinetics, duration, and magnitude of plasma FIX activity, by dose, after IV administration of DTX101 in adults with hemophilia B.	The time course of FIX activity, as determined by aPTT, will be summarized by time point and dose level of DTX101.
To assess the impact of DTX101 on the frequency of FIX replacement therapy during the study.	The annualized and average weekly use of FIX replacement therapy will be calculated for all subjects through Week 52 (± 7 days).
To describe the immune response to the FIX transgene after IV administration of DTX101.	
• The development of neutralizing antibodies to FIX (FIX inhibitor), as determined by a Bethesda assay, will be summarized by time point and dose level of DTX101.• The development of a cell-mediated immune response to FIX, as determined by ELISPOT assay, will be summarized by time point and dose level of DTX101.
To assess the impact of DTX101 on the subject's quality of life	Responses to the EQ-5D-5L and Haem-A-QoL questionnaires will be summarized.

Objective	Endpoint
Exploratory	
To describe the immune response to AAVrh10 capsid proteins after IV administration of DTX101.	
 • The development of neutralizing antibodies to AAVrh10, as determined by ELISA, will be summarized by time point and dose level of DTX101. • The development of a cell-mediated immune response to AAVrh10, as determined by ELISPOT assay, will be summarized by time point and dose level of DTX101. • The development of anti-AAVrh10 binding antibodies, as determined by ELISA, will be summarized by time point and dose level of DTX101.

Abbreviations: AAVrh10, adeno-associated virus serotype rh10; ABR, annualized bleeding rate; ELISA, enzyme-linked immunosorbent assay; ELISPOT, enzyme-linked immunospot; EQ-5D-5L, EuroQoL 5D 5 level; Haem-A-QoL, haemophilia-specific quality of life.

3. Investigational Plan

3.1. Overall Study Design and Plan

Study 101HEMB01 is a Phase I/II open-label, single arm, multicenter, dose-finding safety study in adults with moderate/severe to severe hemophilia B. The primary objectives of the study are to determine the safety of single ascending IV doses and to identify the Optimal Biologics Dose (OBD) of DTX101.

3.1.1. Models and Theoretical Background

The OBD, defined as the dose that is less than or equal to the maximum tolerated dose (MTD) and achieves the efficacy target, will be determined by bCRM. Different from the conventional CRM, bCRM takes into consideration both toxicity and efficacy together. Specifically, two regression models,

$$\log\left(\frac{p_{1j}}{1-p_{1j}}\right) = 3 + \beta_1 x_j,$$

and $\log\left(\frac{p_{2j}}{1-p_{2j}}\right) = 3 + \beta_2 x_j,$

are employed to describe the relationship between toxicity/efficacy and dose. Here, constant alpha for the toxicity regression model is set up as 3 instead of -3 as shown in Braun's paper because it is demonstrated that the model with -3 performs poorly when the

lowest dose is toxic [Tessela 2005], and 3 is the default setting in Fixed and Adaptive Clinical Trial Simulator. p_{1j} is the probability of toxicity seen at dose j , p_{2j} is the probability of efficacy seen at dose j , and x_j is the nominal dose value, instead of real dose values, derived from prior probability estimate of toxicity and efficacy.

The bCRM is implemented as follows. A first cohort of $n = c$ subjects enters the trial on the dose that is most likely the MTD or the lowest dose. Once information on toxicity and efficacy is collected for all c subjects, the posterior mean of p_{1j}^n and p_{2j}^n can be computed for each dose j . Then we can compute the Euclidean distance

$$d_j^n = \sqrt{\sum_{k=1}^2 (p_{kj}^n - p_k^*)^2}$$

for each dose j , where p_1^* and p_2^* are the desired rates of toxicity and efficacy. The dose corresponding to the smallest value of d_j^n is selected, and a new cohort of c subjects enters into this dose. Then p_{1j}^n and p_{2j}^n are updated using all information from $n = 2c$. This procedure is repeated until k cohorts ($n = kc$) have been enrolled. The OBD is defined as the dose that minimize the Euclidean distance after all subjects in the trial are evaluated.

A non-informative prior for the regression parameters β_1 , β_2 and the association between toxicity and efficacy, ω , are set to have the following form:

$$\pi(\beta_1, \beta_2, \omega) = 6 \omega(1-\omega) \exp\{-(\beta_1 + \beta_2)\}, \beta_1 > 0, \beta_2 > 0, 0 < \omega < 1.$$

Here, ω follows a beta (2,2) distribution, β_1 and β_2 follow an exponential (1) distribution. The product of beta and exponential density functions implies marginal independence of all of three parameters and a mean of 1 for each of the two β 's and $\frac{1}{2}$ for ω . Braun [Braun 2002] provides the rationale for this prior: “The prior distribution should be sufficiently defined to offer directions to dose assignment for the first few subjects, but also be sufficiently vague so that the prior distribution's influence on dose assignment decreases as more and more subjects are enrolled.”

3.2. Treatments

Subjects will receive a single, peripheral IV infusion of DTX101. Subjects in the first cohort will start with the lowest dose and subsequent doses will be guided by the results of the bCRM.

The dose of DTX101 to be administered will be calculated using the subject's weight recorded at screening. The subject's weight will be verified prior to administration of DTX101 to ensure that their current weight is within 10% of their screening weight.

4. General Statistical Considerations for Study Result Summarization

4.1. General Presentation of Summaries and Analyses

Modelling to determine the OBD will be conducted using Fixed and Adaptive Clinical Trial Simulator version 4.0.5 [REDACTED] All other general data manipulation and statistical analyses will be conducted using SAS Version 9.2 or higher (SAS Institute, Inc., Cary, North Carolina, United States).

Continuous data will be described using descriptive statistics (ie, n, arithmetic mean, standard deviation (SD), median, minimum, and maximum). Categorical data will be described using the subject count and percentage (n, %) in each category. For descriptive statistics of all numerical variables, unless otherwise specified, the minimum and maximum will be displayed to the same level of precision as reported. Mean and median will be displayed to one level of precision greater than the data collected. SD will be

displayed to two levels of precision greater than the data collected. P-values will be rounded to three decimal places. If a p-value is less than 0.001, it will be reported as “<0.001.” If a p-value is greater than 0.999, it will be reported as “>0.999.”

When count data are presented, the percentage will be suppressed when the count is zero in order to draw attention to the non-zero counts. A row denoted “Missing” will be included in count tabulations where specified in the shells to account for dropouts and missing values. The denominator for all percentages will be the number of subjects within the analysis set of interest, unless otherwise specified.

Change from baseline is the post-baseline value minus the baseline value. If the baseline or post-baseline value is missing, then the change from baseline are set to missing. For each time point where change from baseline is evaluated for continuous variables, descriptive statistics will be displayed for the values at baseline, values at the time point, and values for change from baseline at the time point for the set of subjects who have data at both baseline and the time point being assessed.

Exploratory data analysis (EDA), through descriptive statistics and graphic method, will be conducted for FIX activity throughout the study period.

Imputation will not be performed for all missing values.

Subjects will be identified in the listings by the subject identification number. Data listings will be presented and sorted by subject number, visit, and parameter (where applicable).

Numbering for tables, listings and figures will follow International Conference on Harmonisation E3 Guidelines.

4.2. Analysis Visits

Due to subjects potentially returning outside of the scheduled visits, visit windows will be defined for by-visit summary and analysis purposes.

Only scheduled assessments will be included in the summary tables, which are presented by visit. All assessments (including both scheduled and unscheduled) will be presented in the data listings and figures.

4.3. Definition of Baseline Values and Study Day

Unless otherwise specified, the baseline value for each parameter is defined as the value collected at the time closest to, but prior to, the start of DTX101 administration. The documented history or measurement before Day 0 following the appropriate washout will be used for the baseline values of FIX. For assessments on or after Day 0, the study day will be calculated as assessment date minus date of DTX101 injection (Day 0). For assessments prior to Day 0, the study day will be calculated as the assessment date minus

date of DTX101 injection (Day 0). Study start date is defined as the date the informed consent form (ICF) is signed.

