In nonclinical studies by Nathwani et al, rhesus macaques inoculated with scAAV8-FIX at a dose of 2.0×10^{11} GC/kg expressed a peak of 35% to 40% of normal FIX levels in serum by Day 15 [Nathwani 2011b]. It must be noted that later correction of dosage methods suggested these animals actually received a dose of 2.0×10^{12} GC/kg [Nathwani 2011a]. In comparison, when administered to human patients in a Phase I dose-escalation clinical trial, 2.0×10^{12} GC/kg resulted in sustained average levels of only $5.1 \pm 1.7\%$ of normal FIX activity [Nathwani 2011a; Nathwani 2014]. Based on the corrected dosing, this represents approximately a 10-fold difference in transduction and expression levels between nonhuman primates and humans.

When considering a clinical dosing rationale, in light of the available comparison data between mice, nonhuman primates and humans, it seems reasonable to consider a 100-fold increase in dose from mice to humans to achieve similar target levels of FIX. Therefore, the proposed MED range for human dosing with a target peak expression level of 20% would fall between 1.6×10^{12} and 5.0×10^{12} GC/kg. The proposed initial clinical dose of DTX101 is 1.6×10^{12} GC/kg, 100-fold above the lower end of the MED range in the mouse. Dose escalation would follow at either 3.0×10^{12} GC/kg or 5.0×10^{12} GC/kg. The final dose, 1.0×10^{13} GC/kg, is consistent with a half log increase over the upper end of the proposed human MED range.

A starting dose of 1.6×10^{12} GC/kg has a safety margin of 3-fold versus the no observed adverse effect level (NOAEL) determined in the formal GLP toxicology study (Study 2371-002; refer to section Section 4.4.1.2 of the IB). The primary safety finding from this study was the prolongation of aPTT times that correlated with supraphysiological FIX expression and activity levels. The highest dose tested, 5.0×10^{13} GC/kg, resulted in a peak average prolongation of aPTT of 63% at Day 15. This prolongation began to resolve by Day 29, being 43% at Day 29 and 15% by Day 90. Mice in this dose group (5.0×10^{13} GC/kg) were expressing supraphysiological levels of FIX at more than 2500% of normal.

Although prolongation of aPTT was present, these animals exhibited no related clinical signs or complications. Lower doses of DTX101 resulted in minimal to moderate increases of aPTT that were often not statistically significant.

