3.2.3 Prophylactic Factor IX Washout Periods

3.2.3.1 Screening Period

If the subject does not have a documented history of FIX activity, a blood sample will be needed to confirm the severity of hemophilia B for inclusion ([Section 4.1](#)) after washout of recombinant FIX ([Figure 3–2](#)). For subjects taking long-acting recombinant FIX prophylactically to prevent bleeding episodes, the washout period is to start at approximately Day –29 and last for 21 days (approximately Day –8). For subjects taking traditional recombinant FIX prophylactically to prevent bleeding episodes, the washout period is to start at approximately Day –29 and last for 7 days (approximately Day –22). The blood sample must be obtained and results available prior to dosing on Day 0. Subjects can then transition

back onto their prophylactic regimen until the washout period during the treatment period (prior to Week 6) is to begin ([Section 3.2.3.2](#)).

NOTE: This washout period is not needed for subjects with a documented history of FIX activity.

Figure 3–2**Recombinant FIX Washout During the Screening Period**

Abbreviations: FIX, factor IX.

[figure not shown]
- a. Washout required for subjects that do not have a documented history of FIX activity to meet eligibility criterion (ie, $\leq 2\%$ of normal).
- b. Following assessment of FIX activity, subjects can transition back on to their prophylactic regimen until the protocol mandated washout period prior to the Week 6 assessment of FIX activity.

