8.2.5 Clinical Laboratory Analyses

Laboratory tests, including ALT and coagulation panel, will be closely monitored throughout the duration of the study. Investigators will receive flagged notification of any laboratory values that are outside of the normal range. Any abnormal laboratory test results (hematology, coagulation panel, clinical chemistry, urinalysis, or other laboratory parameters), including those that worsen from baseline or are felt to be clinically significant in the medical and scientific judgment of the investigator, are to be recorded as AEs or SAEs ([Section 9.1.2](#)).

However, any clinically significant safety assessments that are associated with the underlying disease, unless judged by the investigator to be more severe than expected for the subject's condition, are **not** to be reported as AEs or SAEs.

All laboratory tests with results that are significantly abnormal during participation in the study should be repeated until the values return to normal or baseline. If such values do not return to normal within a period judged reasonable by the investigator, the etiology should be identified and the sponsor notified.

Samples of blood, urine, saliva, and stool will be collected for study assessments. Any samples remaining at the end of the study may be stored for up to 15 years and analyzed to better understand the effect of DTX101 on hemophilia B or other related blood disorders. The choice to allow retention and future analysis will be optional.

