10.5.3.2 Clinical Laboratory Assessment Results

For all laboratory assessments with continuous results, absolute values and changes from baseline will be summarized by visit and dosing cohort. For laboratory tests with categorical results, shifts from baseline will be summarized by visit and dosing cohort.

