15.1 Appendix: Schedules of Events

Table 15–1 Schedule of Events – Scheduled Clinic Visits

Procedure	Period	Screening	Dosing	Treatment Period: Week 2 through Week 52 (includes clinic or home visits [see Table 15–2])							Unscheduled	End of Study/Early Withdrawal
	Week	Days –30 to –1	Day 0	2	4	6	8	10	12	16–48 ^a		
	Visit Window (Days)	-	-	±2	±2	±2	±2	±2	±2	±4	-	±7
Informed consent		X										
Demographics		X										
Medical history		X										
Hemophilia history		X										
Prior medication / therapies / procedures		X										
Review of eligibility criteria		X										
FIX genotyping		X										
HLA genotyping		X										
HBV, HCV, and HIV status		X										
FIX inhibitor (Bethesda assay)		X	X ^b			X	X			X ^c	X ^d	X

Procedure	Period	Screening	Dosing	Treatment Period: Week 2 through Week 52 (includes clinic or home visits [see Table 15-2])							Unscheduled	End of Study/Early Withdrawal
	Week	Days -30 to -1	Day 0	2	4	6	8	10	12	16-48 ^a		
	Visit Window (Days)	-	-	±2	±2	±2	±2	±2	±2	±4	-	±7
Coagulation panel (PT/INR, D-dimer assay, aPTT)	X	X ^b	X	X	X	X	X	X	X	X ^d	X	
AAVrh10 neutralizing antibody test (ELISA)	X	X ^b			X	X				X ^c	X ^d	X
Cell-mediated immune response to AAVrh10 and FIX (ELISPOT assay)		X ^b			X	X				X ^c	X ^d	X
AAVrh10 binding antibody IgG assay (ELISA)	X	X ^b			X	X				X ^c	X ^d	X
Saliva, urine, and stool for viral shedding (qPCR) ^f		X ^e	X	X	X	X	X	X	X	X ^d		X
FIX activity (aPTT clot-based assay)	X	X ^b	X	X	X	X	X	X	X	X ^d		X
Hematology / clinical chemistry ^g	X	X ^h	X	X	X	X	X	X	X	X ^d		X
Urinalysis	X		X	X	X	X		X		X ^d		X

Procedure	Period	Screening	Dosing	Treatment Period: Week 2 through Week 52 (includes clinic or home visits [see Table 15-2])							Unscheduled	End of Study/Early Withdrawal
	Week	Days -30 to -1	Day 0	2	4	6	8	10	12	16-48 ^a		
	Visit Window (Days)	-	-	±2	±2	±2	±2	±2	±2	±4	-	±7
12-lead ECG		X	X ⁱ									X
Vital sign measurements (heart rate, blood pressure, respiratory rate)		X	X ^j	X	X	X	X	X	X	X	X	X
Height and weight ^k		X	X ^{b,1}									X ^l
Complete physical examination		X										X
Targeted physical examination ^m			X ^b			X			X	X ⁿ		
AE/SAE monitoring	X	X	X	X	X	X	X	X	X	X	X	X
Concomitant medications / therapies / procedures		X ^b	X	X	X	X	X	X	X	X	X	X
Diary distributed			X									
Diary reviewed				X	X	X	X	X	X	X	X	X
Diary returned												X

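### Baseline aPTT may be measured on infused FIX and Week 6 aPTT off prophylaxis, so its change from baseline is biased toward prolongation in prophylaxis users

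*SAP*

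**What the plan says.** **Baseline.** The general rule in SAP 4.3 is that "the baseline value for each parameter is defined as the value collected at the time closest to, but prior to" the start of dosing. One exception follows: "The documented history or measurement before Day 0 following the appropriate washout will be used for the baseline values of FIX". The aPTT clotting time is not mentioned.

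**Sampling.** In the schedule of events (Protocol 15.1) the coagulation panel, which includes aPTT, is drawn at screening, on Day 0 before dosing, and at the clinic visits from Week 2 to Week 52. FIX activity is drawn at the same visits.

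**Prophylaxis.** Protocol 3.2.3.1 requires a screening washout only of subjects without a documented FIX history. Those who do wash out may go "back onto their prophylactic regimen until the washout period during the treatment period". Under Protocol 3.2.3.2 prophylaxis stops at Week 5 (traditional FIX) or Week 3 (long-acting FIX), ahead of the Week 6 measurement.

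**Use of the baseline.** Protocol 10.5.3.2 reads: "For all laboratory assessments with continuous results, absolute values and changes from baseline will be summarized by visit and dosing cohort". Table 8–1 counts aPTT among the laboratory parameters. Protocol 8.2.5 has abnormal results, the coagulation panel among them, recorded as AEs, "including those that worsen from baseline or are felt to be clinically significant", with an exemption for findings associated with the underlying disease. SAP 9.3 plans a change-from-baseline summary for clinical chemistry only.

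**Why aPTT is watched.** Protocol 1.3.2 says of the GLP toxicology study: "The primary safety finding from this study was the prolongation of aPTT times".

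**The concern.** The SAP avoids an unwashed Day 0 value for FIX, but not for the clotting time that depends on FIX. For a subject on prophylaxis, the aPTT baseline can be taken with infused FIX in the blood and the Week 6 value without it. The difference then combines two things: loss of infused FIX, which lengthens aPTT, and gain of vector-derived FIX, which shortens it in a deficient subject.

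On-demand and prophylaxis patients are both eligible (Protocol 4.1), and cohorts have a minimum of 3 subjects. A by-cohort summary of aPTT change can therefore differ between doses because the cohorts had different mixes of prior regimen. Readers will look closely at aPTT, since prolongation is the named nonclinical finding.

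**Working it through.** The plan states no figure on this point, so there is none to reproduce.

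**Step 1: direction, without numbers.** Let A(off) be a subject's aPTT without infused FIX before dosing, A(0) the Day 0 predose value and A(6) the Week 6 value. Then

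A(6) − A(0) = [A(6) − A(off)] + [A(off) − A(0)].

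The first bracket is the change of interest. The second is the artefact. It is zero with no infused FIX on Day 0, and positive whenever infused FIX shortens aPTT. It does not depend on vector expression. The net change is a prolongation only if Day 0 FIX exceeds Week 6 FIX.

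The documents support the FIX–aPTT link in the deficient range. Protocol 1.3.2 gives 74.3 s for FIX knockout mice, 50 s for controls and 45 s for treated knockouts. Protocol 8.1.1 measures FIX activity by an aPTT clot-based assay.

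**Step 2: illustration of size.** Assumptions, none of them human data: 74.3 s at 1% FIX, 50 s at 100%, log-linear between. The slope is 24.3/2 = 12.15 s per tenfold change:

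aPTT(F) = 50 + 12.15 × (2 − log10 F).

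F = 1, 4, 5, 10, 20% gives 74.3, 67.0, 65.8, 62.15, 58.5 s.

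The artefact A(off) − A(0), for a subject at 1% without infused FIX, is:
- Day 0 FIX 5%: 74.3 − 65.8 = +8.5 s
- Day 0 FIX 10%: 74.3 − 62.15 = +12.15 s
- Day 0 FIX 20%: 74.3 − 58.5 = +15.8 s

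**Step 3: net percentage change, Week 6 against Day 0.** The Week 6 levels are the ends of the mouse MED range (4%, 34%), the mean in the cited human AAV8 trial (5.1%), the target (20%), and 10% as an intermediate assumption. Day 0 levels are assumed.

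| Day 0 FIX | Week 6: 4% | 5.1% | 10% | 20% | 34% |
|---|---|---|---|---|---|
| 1% (no infused FIX) | −9.8 | −11.6 | −16.4 | −21.3 | −25.0 |
| 5% | +1.8 | −0.2 | −5.6 | −11.1 | −15.4 |
| 10% | +7.8 | +5.7 | 0.0 | −5.9 | −10.4 |
| 20% | +14.5 | +12.3 | +6.3 | 0.0 | −4.8 |
| 40% | +22.2 | +19.8 | +13.3 | +6.7 | +1.6 |

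Every row below the first is shifted upward. For Day 0 20% and Week 6 4%, setting the knockout level at 0.5% or 2% instead of 1% changes +14.5% to +12.9% or +16.7%.

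**Step 4: a cohort of 3.** Suppose all three subjects have 4% at Week 6, so the vector result is identical. A subject with no infused FIX on Day 0 shows 67.0 − 74.3 = −7.3 s. A prophylaxis user at 10% on Day 0 shows 67.0 − 62.15 = +4.8 s. Each such user moves the cohort mean by 12.15/3 = 4.05 s:

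| Prophylaxis users in cohort | Mean change (s) |
|---|---|
| 0 | −7.3 |
| 1 | −3.3 |
| 2 | +0.8 |
| 3 | +4.8 |

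Under these assumptions, regimen mix alone can change the sign.

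**The case against.** **The SAP plans no such summary.** SAP 9.3 places aPTT among the other laboratory parameters and names change from baseline for clinical chemistry only. This is correct, and it means the consequence arises through Protocol 10.5.3.2. It does not remove the protocol's commitment; it shows a mismatch that has to be settled anyway.

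**A reader might infer that stopping prophylaxis will appear as prolongation.** The documents do not support that. At the 20% target, Day 0 levels of 5% or 10% still give net shortening (−11.1%, −5.9%), only less than the −21.3% from an off-FIX baseline. Nor do the documents point to high Day 0 levels: the Introduction describes prophylaxis as keeping FIX above 1%, with troughs between doses, and Protocol 6.3 says no FIX is needed for the infusion.

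**A reader might infer that the artefact reproduces the toxicology signal.** It shares the parameter and the direction, not the mechanism. The mouse prolongation (63% at Day 15, 43% at Day 29, 15% by Day 90 at the highest dose) went with FIX above 2500% of normal, whereas the artefact needs Week 6 FIX below the Day 0 level. Knockout mice, which the protocol considers closer to patients, showed shortening, and it calls such prolongation not likely at the starting dose. Because FIX activity is measured at the same visits, the two can be told apart subject by subject, though not from a cohort mean.

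**A reader might infer inflated AE counts.** The underlying-disease exemption in Protocol 8.2.5 plausibly covers a return to the haemophilic aPTT, and DLTs and stopping criteria require investigator-judged relatedness. Nothing applies the SAP 4.3 baseline to those judgments. What stands is only that 8.2.5 does not say which aPTT baseline is meant.

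**Conclusion.** The point holds in limited form. For subjects with infused FIX on Day 0, the aPTT change from baseline under Protocol 10.5.3.2 is biased toward prolongation. It can show false prolongation when Week 6 FIX is below the Day 0 level, and it understates shortening otherwise. Cohort summaries then partly reflect prior regimen.

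The direction rests on the sampling and washout rules, and on aPTT shortening as FIX rises in deficient subjects. The size is unknown. The seconds and percentages above depend on mouse values, an assumed log-linear curve, and assumed FIX levels; neither human aPTT values nor residual FIX on Day 0 are given. Subjects with no infused FIX on Day 0 do not have this bias.

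The issue concerns a descriptive safety summary. The Week 6 FIX endpoint has its own baseline rule and is not affected by it.

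**What to change.** 1. Reconcile SAP 9.3 with Protocol 10.5.3.2, so that it is clear whether aPTT change from baseline is tabulated.
2. In SAP 4.3, use a screening aPTT as baseline only if it was drawn after completed washout. Nothing ties the screening coagulation sample to the end of washout, and screening may span several days, so this must be checked against recorded FIX-use dates. Protocol 3.2.3.1 and the schedule footnote agree on washout length (7 and 21 days) but not on the start days; the two should be reconciled.
3. For all other prophylaxis users, keep the Day 0 value and flag it as on-FIX. Dropping their change from baseline could empty a cohort of 3.
4. Present aPTT change separately for subjects on and off infused FIX at Day 0, and show absolute aPTT beside same-visit FIX activity and time since the last FIX infusion. This also covers later visits, where on-demand use or resumed prophylaxis is possible.
5. State in Protocol 8.2.5 which baseline applies when worsening of aPTT is judged.

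The cost is SAP wording, a short protocol clarification and one extra table split. Same-visit FIX activity and FIX use are already collected. The downside is smaller subgroups in a table that is already descriptive.
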